### 8.1.1. Primary Analysis

The MIRASOL vs CONTROL group will be compared with respect to the number of days of WHO grade 2 or higher bleeding. This will be carried out by fitting a negative binomial regression model with an offset defined as the natural logarithm ( $\ln$ ) of the number of days that bleeding was assessed in order to account for the fact that subjects may have different numbers of bleeding assessment days. As an example, if a subject had bleeding assessed on only 10 of 28 days, an “offset” of  $\ln(10)$  bleeding assessment days is incorporated into the linear predictor of the model. Similarly, if bleeding is assessed on each of the full 28 days of the planned treatment period, an offset of  $\ln(28)$  bleeding assessment days is incorporated. Adjustment using this offset will ensure that bleeding *rates* are calculated and compared between treatment groups and that the variable number of days with bleeding assessments across individuals is appropriately dealt with. Subjects who obtain transfusion independence prior to Day 28 will be assumed to have zero bleeding days between the date of transfusion independence and Day 27 and treated as if they had bleeding assessed on each of those days; these days will therefore contribute to the total number of bleeding assessment days used to calculate the offset. Subjects who drop-out of the study before Day 28 for reasons other than transfusion independence will contribute bleeding data for each of the days bleeding was assessed prior to the time of drop-out; bleeding status will not be simulated beyond the time of drop-out since the use of an appropriately computed offset deals with the variable duration of follow-up.

The handling of data following the administration of an off-protocol transfusion requires discussion. Here an off-protocol transfusion is defined as the transfusion of any kind of PLT product that differs from that to which the subject was randomized (i.e. MIRASOL or CONTROL).

The timeline diagram provided below demonstrates the definition of an off-protocol window, which we sometimes refer to as an off-protocol interval of time. Consider an individual who was recruited and received on-protocol transfusions as needed from day 0 to day  $n-1$ . On Day  $n$  they received an off-protocol transfusion and on Day  $m$  they received their first subsequent on-protocol transfusion; no off-protocol transfusions were received beyond Day  $m$ . In order to avoid attributing bleeding outcomes to the randomized treatment arm when an off-protocol product is delivered we partition the full treatment period as follows. We define the intervals from day 0 to  $n-1$  and  $m$  to Day 27 as *on-protocol intervals*, and days  $n$  to  $m-1$  as an *off-protocol interval*. In the figure below bleeds are represented by red lines on Days 1-2 and on Day 26 for illustration.

To mitigate against the effect of the off-protocol transfusions in the primary endpoint analysis, bleeding data will be simulated for the off-protocol windows (e.g. intervals such as  $[n, m-1]$  above) using an

individual-specific bleeding rate estimated as follows. If individual  $i$  has any off-protocol intervals of time, then an individual-specific bleeding rate will be computed as  $r_i^{on} = B_i^{on} / N_i^{on}$  where  $B_i^{on}$  is the number of on-protocol days during which this individual experienced, and had documented, at least WHO grade 2 or higher bleeding.  $N_i^{on}$  is the number of days on which bleeding was assessed during the on-protocol intervals for this subject. Then a) the number of days bleeding was assessed during the off-protocol interval will be computed ( $N_i^{off}$ ) and b) the number of these days during which WHO  $\geq 2$  grade bleeding is present will be simulated ( $B_i^{off}$ ) based on a right-truncated Poisson distribution using the individualized bleeding rate ( $r_i^{on}$ ). The right-truncation limit will be the total number of off-protocol days ( $N_i^{off}$ ) since there cannot be more bleedings days than there are days at risk. Specifically, for each individual, counts will be simulated from a Poisson distribution using  $r_i^{on} \times N_i^{off}$  as the mean. A simple rejection sampling technique [1] will be used to sample from the right-truncation distribution whereby all values generated which exceed the right truncation limit will be ignored until one is generated that satisfies the right truncation condition. This value will be labelled  $B_i^{off}$ . Then the total  $B_i^{on} + B_i^{off}$  will be taken as the number of bleeds for that individual experienced over  $N_i^{on} + N_i^{off}$  days of assessments; then  $\ln(N_i^{on} + N_i^{off})$  will be used as the offset.

If the bleeding rate estimated based on available data  $r_i^{on} = 0$  then there will be no bleeding days simulated for the off-protocol days ( $B_i^{off} = 0$ ) and the offset will still be calculated as  $\ln(N_i^{on} + N_i^{off})$ . Note that for individuals whose last transfusion is off-protocol, at most 10 days of bleeding data after the last transfusion will be simulated as patients going ten (10) days without a transfusion will have acquired transfusion independence.

On occasions where a subject receives a mix of off-protocol and on-protocol units on the same day, they will be considered in an on-protocol period on that day. Transfusions can last more than one calendar day. The daily on- and off-protocol statuses will be assigned for the day the transfusion(s) starts. For subjects whose last transfusion is off-protocol, bleeding will be simulated until the subject completes the transfusion period or reaches transfusion independence. If the subject achieves transfusion independence prior to completing the transfusion period, the rules for transfusion independence will take over and subjects will be assumed to have zero bleeds and full follow-up from the day of transfusion independence until Day 27 inclusive (i.e. the remainder of the transfusion period).

Unless otherwise stated any subsequent analysis herein referring to the primary endpoint method will include the individualized simulated bleeding data for the off-protocol periods of time. This simulation will be done twice. Once at the IA and once at the final analysis. The set of simulations done for the primary efficacy analysis will be used for all subsequent analyses wherein off-protocol intervals are called to use simulated bleeding data.

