## 7.7. Calculation of Study Day and Treatment Period

The day the subject receives their first post-randomization PLT transfusion will be considered Day 0. If the subject's PLT transfusion episode spans two calendar days, the day the transfusion started will be considered Day 0.

The treatment period is defined as the period of time from Day 0 through Day 27 or to the day of transfusion independence, defined as the last of ten (10) successive days after the last PLT transfusion (on- or off-protocol), whichever occurs first. Bleeding assessments are conducted at baseline and are to be conducted every day from Day 0 until the post-transfusion follow-up visit or early termination visit.

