## 8. Efficacy Analysis

A single primary efficacy endpoint will be considered and investigated using a NI design. The primary efficacy endpoint is defined as the number of days on which bleeding was assessed and WHO grade 2 or higher bleeding was evident over the treatment period. The maximum number of days with bleeding assessments will be twenty-eight (28) as this is the duration of the treatment period. Bleeding events are defined using criteria according to the WHO Grading Scale for Bleeding. Appendix I contains the WHO Grading Scale for Bleeding annotated with the study's Bleeding Assessment (MIPLATE Annotated eCRFs) variable identifiers (Bx) and answers that correspond to the bleeding status. Subgroup analyses involving the primary efficacy endpoint will also be conducted.

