### 8.1.2. Secondary Analyses

#### First Secondary Analysis: Off-Protocol Intervals Included with No Adjustments

In a secondary analysis of the primary outcome all available bleeding assessment data, whether collected on- or off-protocol, will be used and attributed to the randomized treatment in the spirit of an intention to treat analysis. No imputation will be carried out for bleeding status on days following drop-out as the offset deals with censoring and the resulting variation in the days at risk.

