#### Second Secondary Analysis: Off-Protocol Intervals Excluded

In another secondary analysis of the primary outcome, bleeding data will be excluded during off-protocol intervals and the offset will be computed based on the number of on-protocol days which bleeding was assessed for the negative-binomial model. Subjects who obtain transfusion independence while on-protocol will be assumed to experience no further WHO grade 2 or higher bleeding and treated as if they

had bleeding assessed on each of those days. No bleeding data will be imputed following dropout if it occurs and the offset will accommodate different durations of time at risk.

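### The offset does not by itself handle drop-out before transfusion independence: zero-filling after independence breaks the constant-rate condition, so unequal drop-out between arms would shift the non-inferiority ratio by a few percent

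*SAP*

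**What the plan says.** SAP section 8.1.1 (the file supplied as the protocol carries the same text) fits a negative binomial model with ln(assessed days) as offset and has two rules for incomplete follow-up.

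- **Subjects who reach TI** "will be assumed to have zero bleeding days between the date of transfusion independence and Day 27", and "these days will therefore contribute to the total number of bleeding assessment days used to calculate the offset". TI is the tenth day after the last platelet transfusion (section 7.7).
- **Subjects who leave for another reason** contribute only the days actually assessed: "bleeding status will not be simulated beyond the time of drop-out", on the ground that "the use of an appropriately computed offset deals with the variable duration of follow-up".

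Section 8.1.2 repeats the argument. The First Secondary Analysis says "the offset deals with censoring and the resulting variation in the days at risk", and the Second says "the offset will accommodate different durations of time at risk". The First Sensitivity Analysis imputes missing on-protocol days 50 times from a negative binomial model with age, sex, arm, treatment-type stratum and pre-treatment platelet count. It does not say whether days after drop-out are included.

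**The concern.** The offset makes follow-up of different lengths comparable only when the expected daily rate is the same throughout. Here the rate is positive while the subject is transfusion-dependent and is set to zero from TI. A subject who leaves before TI supplies only days from the first phase. One who stays supplies both. Their fitted rates differ even if they bled identically while dependent and the departure had nothing to do with bleeding.

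The plan recognises the two phases elsewhere: the interim simulation in section 8.6 generates bleeding over the dependent period and sets zero from TI onward.

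At stake is the only confirmatory comparison, tested at one-sided 0.025 against a ratio of 1.6. The arm that loses more subjects before TI looks worse than it is. Heavier loss in CONTROL makes a false non-inferiority claim easier. Heavier loss in MIRASOL makes a true one harder to show.

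**Working it through.** **Inputs from the SAP.** Margin 1.6 (8.1.3); one-sided alpha 0.025 (6.3.1); 558 mITT subjects, so 279 per arm, with 85% power at a true ratio of 1.1 (6.3.3); 28 assessment days (8).

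**Inputs not given, so assumed.** TI day; drop-out before TI by arm; CONTROL mean μ_C of 1 to 4 bleeding days per 28; dispersion φ. The 10% in section 6.3.3 concerns subjects never transfused, who are outside the mITT set.

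**1. The plan's power figure.** It cannot be reproduced without μ_C and φ, but it fixes the standard error:

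SE = ln(1.6/1.1)/(1.960 + 1.036) = 0.3747/2.996 = 0.125.

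With SE² = (1/μ_C + 1/μ_T + 2φ)/279 and μ_T = 1.1 μ_C, this gives φ = 1.23, 1.70 or 1.94 for μ_C = 1, 2 or 4. These pairs are used below.

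**2. Factor for one subject.** Let the daily rate be r on each day before TI, and zero after. A subject who stays has r × TI bleeding days over 28. One who leaves on day d before TI has r × d over d. The ratio of the two rates is 28/TI.

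- TI Day 17 (last transfusion Day 7): 28/17 = 1.65
- TI Day 20 (last transfusion Day 10): 28/20 = 1.40
- Earliest TI, Day 10: 2.8; TI on Day 27: 1.04; against completers who never reach TI: 1.0
- If 30% never reach TI (assumed), the average factor is 1/(0.7 × 17/28 + 0.3) = 1.38 for Day 17 and 1/(0.7 × 20/28 + 0.3) = 1.25 for Day 20

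**3. Shift in the arm ratio.** In large samples each arm's fitted daily rate λ solves Σ(y − λt)/(1 + φλt) = 0, with t = 28 for those who stay and t uniform over the days before TI for those who leave.

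Worked case with μ_C = 2, φ = 1.70, TI Day 17, true ratio 1.1:

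- Drop-out 15% MIRASOL, 5% CONTROL: fitted 28-day means 2.341 and 2.040, ratio 1.148 = 1.1 × 1.044. Power = Φ((ln 1.6 − ln 1.148)/0.125 − 1.96) = 76%.
- Drop-out 5% MIRASOL, 15% CONTROL: 2.245 and 2.126, ratio 1.056 = 1.1 × 0.960. At a true ratio of 1.6 the same factor gives Φ(−ln 0.960/0.125 − 1.96) = 5.1%.

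Across μ_C = 1 to 4, if everyone who stays reaches TI on the stated day:

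| TI day (assumed) | 28/TI | Shift, 15% MIRASOL vs 5% CONTROL | Power at 1.1 | Shift, 5% vs 15% | False non-inferiority at 1.6 |
|---|---|---|---|---|---|
| 12 | 2.33 | 1.058 to 1.095 | 72 to 62% | 0.948 to 0.916 | 6.2 to 10.4% |
| 17 | 1.65 | 1.035 to 1.050 | 78 to 74% | 0.968 to 0.953 | 4.5 to 5.7% |
| 20 | 1.40 | 1.023 to 1.032 | 80 to 78% | 0.978 to 0.970 | 3.7 to 4.3% |
| 24 | 1.17 | 1.011 to 1.014 | 83 to 82% | 0.990 to 0.987 | 3.0 to 3.2% |

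With 10% drop-out in both arms and TI on Day 17 or 20, the shift is below 0.1% at a true ratio of 1.1.

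**4. Simulation.** With 279 per arm and a true ratio of 1, 5% vs 15% drop-out (MIRASOL vs CONTROL) gave about 0.96 to 0.98, the reverse gave 1.04 to 1.06, and balanced drop-out gave about 1.00.

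**5. What completion does.** In 400 simulated trials per case at true ratio 1.1 with 15% vs 5% drop-out, completing every subject to 28 days (same rate before TI, zero after) moved the mean ratio from 1.145 to 1.096 for TI Day 17 and from 1.128 to 1.097 for Day 20. Power moved from 71.5% to 84.0% and from 76.2% to 85.8%. The Monte Carlo standard error of these power figures is about 2 points (√(0.8 × 0.2/400) = 0.02).

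**6. Whether a planned analysis removes it.** The Poisson and per-protocol repeats keep the same offset. The imputation model has no study-day or TI term. Filling lost days at the subject's own rate leaves that rate unchanged, so it removes nothing; filling them at a common arm rate removed only about a third of the shift when simulated.

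**The case against.** The best defence is that the effect is conditional and modest. No imbalance in drop-out is documented, balanced drop-out cancels, subjects who leave after TI are zero-filled like everyone else, and a shift of 2 to 6% is small beside a standard error of 0.125. All of that stands. It limits the size of the problem but does not make the stated rationale correct.

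A second defence is that the First Sensitivity Analysis already covers the gap, since section 8.1.1 draws on-protocol intervals as running to Day 27. That reading is possible. A reader might go the other way and infer that this analysis fills missing days at one constant rate; the text does not say so, since it names a model with covariates. What stands is narrower: inclusion of days after drop-out is unstated, and no listed covariate tracks time or TI.

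Third, the First Secondary Analysis does not mention zero-filling, so its wording alone does not establish the mechanism there. The Second applies zero-filling only when TI is reached on-protocol. This stands; those two passages matter for the repeated offset claim.

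Finally, the Clinical Investigation Plan was not supplied, so any drop-out or bleeding assumptions in it could not be checked.

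**Conclusion.** The statement that the offset takes care of drop-out is wrong under the plan's own rules for subjects who leave before TI, and no planned analysis clearly corrects for it. With a 10-point difference in such drop-out and TI around Day 17 to 20, the ratio moves about 2 to 6%. False non-inferiority becomes roughly 4 to 6% instead of 2.5%, or power 74 to 80% instead of 85%, depending on which arm loses more. The effect is larger with earlier TI. It is smaller with later TI or when many subjects never reach TI. These figures assume a level bleeding rate before TI and drop-out unrelated to bleeding.

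Two stronger readings are not supported. A reader might take 1.40 to 1.65 as a property of this trial; it is only the case of TI on Day 17 to 20, and a last transfusion on Day 11 already gives 28/21 = 1.33. It is also a factor for one subject, not the shift in the ratio. A reader might also infer that the trial is biased towards non-inferiority. The documents give no drop-out by arm, so neither the presence nor the direction of a shift is established.

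**What to change.** - **Wording.** In section 8.1.1, and in the similar sentences of the First and Second Secondary Analyses, say that the offset accounts for unequal follow-up only if the daily bleeding rate is constant over the period.
- **First Sensitivity Analysis.** State that days after drop-out before TI are imputed to Day 27, and make the imputation depend on study day and TI status. One way is to draw the remaining days and the TI day from same-arm subjects still transfusion-dependent on that day, within treatment-type stratum where donor numbers allow, combined over the 50 imputations already planned.
- **Deaths.** Keeping deaths before TI as observed leaves the same distortion for them, so show the result both ways: as observed and completed.
- **Reporting.** Tabulate drop-out and death before TI by arm. Report whether the upper bound stays below ln(1.6) as a sensitivity result beside the unchanged primary analysis.

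The cost is SAP text and some programming on data already collected. The completion assumes that subjects who leave resemble same-arm subjects still dependent on that day, and donor pools may be thin late in the period.

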### 6.3.1. Primary Endpoint

The primary study objective will be assessed through examination of the Primary Efficacy Endpoint where clinical effectiveness will be measured by comparing the days of grade 2 or higher bleeding over the treatment period between the MIRASOL and CONTROL groups. Specifically, this study will investigate whether MIR-treated Aph PLTs (MIRASOL) are non-inferior to conventional PLTs (CONTROL) by testing the null hypothesis that the MIRASOL arm is inferior to the CONTROL arm. The null hypothesis will be tested using a one-sided alpha level of 0.025. If NI is established, superiority of MIR-treated Aph PLTs vs Conventional PLTs will be tested using a one-sided alpha level of 0.025 by employing a closed “gate keeper” multiple testing strategy. An in-depth discussion of the analysis of the primary efficacy endpoint is provided in Section 8.1 of this document.

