### 6.3.3. Sample Size

A total of approximately 558 mITT subjects will be randomized in a 1:1 fashion to MIRASOL:CONTROL. This sample size estimate accounts for 10% of subjects who are randomized but will never receive an on-study transfusion and thus, will not be included in the mITT analysis set and, therefore, the primary analysis. A total of 558 mITT subjects in MIRASOL versus CONTROL will provide approximately 85% power for establishing non-inferiority at the 1-tailed 0.025 level of significance (using a 2-sided 95% CI) accommodating a 10% relative increase in the mean rate of WHO grade 2 or higher bleeding (i.e.  $\mu_T / \mu_C = 1.1$ ).

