### 8.1.3. Assessment of Non-Inferiority and Superiority

An NI analysis will be carried out to assess the primary efficacy endpoint with the null hypothesis being the MIRASOL arm is inferior to the CONTROL arm and the alternative hypothesis being the MIRASOL arm is non-inferior to the CONTROL arm. The null ( $H_0$ ) and alternative ( $H_a$ ) hypotheses are defined as:

$$H_0: \frac{\lambda_T}{\lambda_C} \geq \delta \text{ and } H_a: \frac{\lambda_T}{\lambda_C} < \delta \text{ respectively}$$

where  $\lambda_T$  is the mean rate of the MIRASOL group,  $\lambda_C$  is the mean rate of the CONTROL group, and,  $\delta$  is the NI margin. To facilitate analysis, the null and alternative hypotheses are expressed on the natural logarithmic scale and take on the following forms.

$$H_0: \ln(\lambda_T) - \ln(\lambda_C) \geq \ln(\delta) \text{ and } H_a: \ln(\lambda_T) - \ln(\lambda_C) < \ln(\delta)$$

Specifically, a 95% confidence interval (CI) will be created about the point estimate (equivalent to a one-sided CI with an alpha level of 0.025) to test the null hypothesis, where the point estimate is defined as  $\ln(\lambda_T) - \ln(\lambda_C)$ . This parameter estimate will be obtained by fitting a negative binomial regression model with a natural log link, the response being the total number of WHO  $\geq 2$  grade bleeding days, a single treatment covariate which is 1 for individuals assigned to the MIRASOL product and 0 for those assigned the CONTROL, and with an offset of the  $\ln(\text{number the number of days bleeding was assessed})$ .

If the upper bound of the 95% CI is less than  $\ln(\delta)$ , then, NI of the MIRASOL arm relative to the CONTROL arm is inferred. Conversely, if the upper bound of the 95% CI is greater than or equal to  $\ln(\delta)$ , NI is not demonstrated. In this study, the NI margin is 1.6. Justification of the value of 1.6 for the NI margin is provided in the CIP.

If NI is demonstrated, superiority of the MIRASOL arm versus the CONTROL arm will be examined. Superiority of the MIRASOL arm compared to the CONTROL arm will be demonstrated if the upper bound of the 95% CI is less than zero ( $\ln(1)=0$ ).

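### For switching subjects who bled on-protocol, the truncated Poisson draw in the primary analysis imputes fewer off-protocol bleeding days, on average, than r_on × N_off; the effect on the rate ratio is small

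*SAP*

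**What the plan says.** SAP section 8.1.1 does not use the bleeding observed after an off-protocol transfusion: "To mitigate against the effect of the off-protocol transfusions in the primary endpoint analysis, bleeding data will be simulated for the off-protocol windows". For each subject with off-protocol time the steps are:

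- r_on = B_on / N_on, the share of assessed on-protocol days with grade 2 or higher bleeding.
- A Poisson count with mean r_on × N_off, right-truncated at N_off because bleeding days cannot exceed days at risk.
- Truncation by rejection: "all values generated which exceed the right truncation limit will be ignored until one is generated that satisfies the right truncation condition".
- The accepted value B_off is added to B_on, and the offset is ln(N_on + N_off), so every off-protocol day counts as exposure.
- If r_on = 0, B_off is set to 0.

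The limit is described as the subject's total off-protocol days, with counts simulated per individual. The same section says the simulation is done once at the interim and once at the final analysis, and that later analyses needing simulated off-protocol data reuse that set. The first two secondary analyses in section 8.1.2 do not use the draw: one takes all observed bleeding, the other drops the off-protocol intervals.

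**The concern.** The procedure is meant to carry the subject's own on-protocol rate into the off-protocol window. For that, the imputed count should average r_on × N_off over N_off days. Rejection discards only draws that are too high, so the accepted draws average less, while the exposure is not reduced to match. A subject with r_on > 0 therefore enters the model with an imputed daily rate below r_on.

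This comes from the distribution, not from drawing once. Repeating the draw or fixing the seed would leave it in place. Analyses that reuse the simulated set inherit it: the missing-data sensitivity analysis (8.1.2) and the subgroup analyses (8.1.5). So does the per-protocol repeat of the primary process (8.1.4).

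In a non-inferiority trial, a one-directional loss of events deserves attention if it could fall more heavily on the test arm. Section 7.12 makes that plausible. A 'Control Allowed' product is not non-compliant for a MIRASOL subject, whereas anything other than 'Control Allowed' is non-compliant for a CONTROL subject.

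**Working it through.** **Inputs from the SAP.** "The null hypothesis will be tested using a one-sided alpha level of 0.025" (6.3.1); "A total of approximately 558 mITT subjects will be randomized in a 1:1 fashion to MIRASOL:CONTROL", so 279 per arm (6.3.3); "85% power for establishing non-inferiority at the 1-tailed 0.025 level of significance" (6.3.3), "accommodating a 10% relative increase in the mean rate of WHO grade 2 or higher bleeding", a true ratio of 1.1 (6.3.3); "In this study, the NI margin is 1.6" (8.1.3). The control bleeding rate, the negative binomial dispersion, the switching frequencies and the window lengths are not stated, so they are assumptions below.

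**1. The plan's power figure, for scale.** Power = Φ[(ln 1.6 − ln 1.1)/SE − 1.960], with SE² = 2v/279 and v = 1/μ + φ. Without μ and φ the 85% cannot be reproduced independently: μ of 1 to 5 days and φ of 0.5 to 4 give 51% to nearly 100%. Solving backwards, SE = 0.3747/(1.960 + 1.036) = 0.125, and v = 0.125² × 279/2 = 2.18.

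**2. Mean of the accepted draw.** With λ = r_on × N and N = N_off, E[X | X ≤ N] = λ · P(X ≤ N − 1)/P(X ≤ N). The ratio of probabilities is below 1 whenever λ > 0. By hand (the factor e^−λ cancels):

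- r = 1, N = 1: 1 × 1/2 = 0.50. In general, N = 1 gives r/(1 + r).
- r = 0.5, N = 2: 1 × 2/2.5 = 0.80.
- r = 1, N = 3: 3 × 8.5/13 = 1.96.
- r = 0.1, N = 3: 0.3 × 1.345/1.3495 = 0.299.

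| r_on | N_off | r_on × N_off | Truncated mean | Loss |
|---|---|---|---|---|
| 0.1 | 3 | 0.30 | 0.299 | under 1% |
| 0.3 | 5 | 1.5 | 1.479 | 1.4% |
| 0.5 | 2 | 1.0 | 0.80 | 20% |
| 0.5 | 3 | 1.5 | 1.299 | 13.4% |
| 0.5 | 10 | 5 | 4.908 | 1.8% |
| 1 | 1 | 1 | 0.50 | 50% |
| 1 | 3 | 3 | 1.96 | 35% |
| 1 | 10 | 10 | 7.854 | 21.5% |

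Rejection sampling reproduced the formula (for example 1.2986 against 1.2985 at r = 0.5, N = 3).

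**3. Effect on the rate ratio, under assumed switching.** Daily bleeding was simulated over 28 days as beta-binomial, with heterogeneity set so that v is about 2.18 in the control arm. The planned negative binomial model with offset was fitted, at a true ratio of 1.1. Entries compare a Binomial(N_off, r_on) draw with the truncated Poisson.

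| Mean daily rate | Switching MIRASOL/CONTROL | N_off | Binomial | Truncated Poisson | Shift |
|---|---|---|---|---|---|
| 0.05 | 30%/5% | 1–3 | 1.1000 | 1.0992 | 0.001 |
| 0.1 | 30%/5% | 1–3 | 1.1015 | 1.0989 | 0.003 |
| 0.1 | 30%/5% | 3–10 | 1.1069 | 1.1049 | 0.002 |
| 0.1 | 60%/5% | 5–15 | 1.0973 | 1.0930 | 0.004 |
| 0.2 | 30%/5% | 1–3 | 1.1050 | 1.0996 | 0.005 |
| 0.2 | 30%/5% | 3–10 | 1.0992 | 1.0912 | 0.008 |
| 0.2 | 60%/5% | 5–15 | 1.0959 | 1.0759 | 0.020 |
| 0.1 | 30%/30% | 3–10 | 1.0965 | 1.0963 | under 0.001 |
| 0.2 | 30%/30% | 3–10 | 1.0980 | 1.0975 | under 0.001 |

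In one further cell (rate 0.05, 30%/5%, N_off 3–10) the drawn count was 1.005 of its target. That cannot be true in expectation, so the smallest shifts are within simulation noise.

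A second set used 150 trials per scenario, 279 per arm, 20% or 40% MIRASOL against 2% CONTROL switching, and a daily rate near 0.12 while dependent. It gave 1.031 against 1.025 and 1.048 against 1.036 with r_on from dependent days, and 0.990 against 0.988 and 0.961 against 0.961 with r_on from all on-protocol days.

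**4. Against the standard error.** A shift of 0.004 on 1.1 is 0.0036 on the log scale, or 0.0036/0.125 = 0.03 SE. The extreme case is ln(1.0959/1.0759) = 0.0184, or 0.15 SE.

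**5. At the margin.** With a true ratio of 1.6 and 400 trials, the extreme setting gave 1.6102 (binomial) against 1.5757. Non-inferiority was declared in 5.2% and 8.2% of trials, and in 6.0% with the true off-protocol data. Across the four settings run, the true data themselves gave 5.0% to 6.8% instead of 2.5%. The standard-error approximation is therefore too rough, and the runs too few, to quantify a type I error change.

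**The case against.** The strongest reply is that the plan openly names a right-truncated Poisson, gives its reason, and never says that the accepted value averages r_on × N_off. That is correct: the target is inferred from the plan's aim, and there is no contradiction in the text. But an imputed rate below r_on, over a full count of days, is not what carrying the individual rate forward would give.

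The largest percentages also need few off-protocol days in total. The limit is most naturally read as the subject's total, so separate one-day windows are pooled (a singular 'interval' nearby leaves some doubt), and mixed-product days count as on-protocol. The percentages apply to the imputed part, not to the subject's whole count. All of this stands.

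The two secondary analyses that avoid the draw should show any material distortion. They would help, but they do not repair the primary estimate.

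A reader might infer that every switching subject loses bleeding days, or that the primary comparison is tilted toward non-inferiority. The documents support neither. Subjects with r_on = 0 receive exactly r_on × N_off = 0. The shortfall is relative to the carried-forward rate, and nothing shows whether bleeding observed off-protocol is higher or lower. The rule is identical in both arms, and section 7.12 permits more MIRASOL switching without giving a frequency.

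**Conclusion.** The point holds in limited form. For switching subjects with r_on > 0, the expected imputed count is below r_on × N_off while the offset keeps all N_off days; this follows from section 8.1.1 alone. The loss is at most 1.4% at r_on of 0.3 or less with N_off of 5 or more. It is material for frequent bleeders or very few total off-protocol days.

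The rate ratio moves only if switching or bleeding rates differ by arm, and toward non-inferiority if MIRASOL subjects switch more. Its size rests on assumed switching shares, window lengths and bleeding rates: usually 0.001 to 0.004 on a ratio of 1.1, 0.005 to 0.008 at a daily rate of 0.2 with 30% against 5% switching, and about 0.02 in the extreme setting. No changed conclusion or type I error has been shown. This is a desirable correction, not a threat to the trial.

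**What to change.** In section 8.1.1, replace the truncated Poisson with B_off ~ Binomial(N_off, r_on), at both the interim and the final analysis. Its mean is exactly r_on × N_off, it cannot exceed N_off, it gives zero when r_on = 0, and it needs no rejection step. In the large-sample runs at a true ratio of 1.1 it gave the same ratio as the true off-protocol data to within about 0.002. State in the same sentence that N_off is the subject's total assessed off-protocol days.

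The cost is one sentence and one line of code. The minor downside is that at r_on = 1 the draw has no variance, even when r_on rests on few on-protocol days. If the truncated Poisson is kept, state the expected shortfall and show the two secondary analyses that avoid the draw beside the primary result.
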